### 9.1.4 Test Subject Recruitment:

[Note: This material is adopted from former protocol C-L-001]

### 9.1.4.1 Synopsis of Recruitment Process:

- i) Source(s): Participants are recruited by verbal networking through our academic and personal communities of friends, neighbors and scientists in Davis, California. Individuals are recruited from the community specifically for each study. Studies are not conducted with individuals from particular employers or agencies.
- ii) Initial Contact Method: Initial contact is through word-ofmouth and telephone contact with individuals in our Volunteer Data Base.
- iii) Follow up Contact Method: Telephone interview, personal interview with the Study Director conducted at the Carroll-Loye Biological Research Offices.

#### 9.1.4.2 Methods of Recruitment:

Our subjects are mainly University of California—Davis graduate and undergraduate students in life science programs with which the Principal Investigator is associated. Students in his laboratory who depend on him directly for employment or scholastically are not eligible to participate. Other subjects are science, education and health care professionals, and mosquito and vector control professionals.

We contact subjects who participated in previous Carroll-Loye repellent efficacy tests by selecting them from our Volunteer Database. At that time interested individuals often ask if one or more of their lab mates or acquaintances may participate as well. All such potential participants are screened or re-screened for suitability for each test in a private, one-on-one conversation held at the office of the Study Director. The Exclusion Criteria (section 9.1.2) are exercised by asking each candidate to address them in the interview with the Study Director. It is explained that pregnancy will be assessed directly in on the test day. The Study Director encourages candidates to ask questions and ask for clarification at any time during the interview and in all activities

that follow. To candidates that pass screening the Study Director describes the test purpose in plain language (in English), and the procedures and comportment to be followed are described in detail. Candidates are then asked if they would like to retire from consideration at that point. If they wish to remain in consideration, it is explained and emphasized that they may withdraw from the test at any time during the test without penalty to their compensation. Candidates are given copies of the State of California Department of Pesticide Regulation 'Experimental Subjects' Bill of Rights' to read as the Study Director reads it aloud. They are also given a copy of the IRB-approved consent form to read as the Study Director reads it aloud. The amount and form of compensation is described. They are again encouraged to ask any questions they have about the test, which may include understanding its purpose more fully, understanding risks and discomforts more fully, and understanding treatment and compensation for injury more fully. While the majority of our subjects have worked with us on an occasional basis for a number of years, we encourage them to personally evaluate their interests and concerns about participation seriously each time. We ask them not to sign on immediately but to give the situation due consideration (normally at least one day, sometimes less for those who have participated in multiple prior studies). Because most of the volunteers are researchers and/or have advanced degrees in life sciences, we regard their motivations and decisions to participate as being unusually well considered and well informed. Accordingly, we normally accept their decisions to participate if they so choose following due consideration. Nonetheless, the Study Director retains the final right to refuse participation to any candidate.

#### 9.1.5 Identification method and records retention:

Subjects will initially be identified by first and last name, and assigned a unique number for purposes of this study. Individual data will be entered into the computer for retention and analysis with reference to individual number, not name. Records relating individual names to individual numbers will be retained separately. The Study Director will retain records indefinitely. Subjects may obtain their own records from the Study Director.

# **9.1.6** Enrollment of alternate subjects and its relation to individual privacy:

We will enroll three more subjects than are required to meet our sample size. All subjects will be informed during the Consent process that on the day of testing, a small number of subjects may be designated as alternates and sent away after being compensated for coming to the test site. Alternate subjects may return later to replace subjects that initiate testing but withdraw before useful data are generated. They also serve as insurance against any enrolled subjects who fail to appear.

The possibility that any subject may be designated as an alternate will assist in protecting the privacy of any subject that must withdraw in or near the presence of other subjects at the start of the test day (i.e., before treatment and testing begins), for reasons such as a positive pregnancy test result, or for any other personal circumstance to which possibly inappropriate attention might otherwise more readily be drawn. In the case of privacy concerns related to pregnancy detection, we regard this "indirect" approach as potentially as discrete and less likely to result in errors that would be the case if we were to employ, e.g., separate male and female Informed Consent Forms, with pregnancy only mentioned on the female form. The latter approach does not address loss of privacy among females, nor does it control the possibility of indiscrete revelation of pregnancy testing by females to males during the test or later, and it also creates the risk of a female subject using the wrong form. Separate forms would also assume that we may fairly treat individual subjects unequally on the basis of postulated genderbased differences in the information the merit receiving in to arrive at their informed consent decision. The soundness of making such an assumption enters ethically complex grounds requiring an intricacy of analysis and breadth of treatment beyond the scope appropriate to the privacy concerns of the present study.

# 9.2 Blinding of Study:

# 9.2.1. Extent of the Blinding:

The types of Test Materials and their identities will be evident to subjects as they apply them during the dosimetry portion of the study. During the repellency portion of the study, subjects will be blinded to the exact treatments they receive although some may note differences between the lotions and the clear liquids in the repellency potion of the study. The Study Director will be blinded to the identity of individual treatments until the conclusion of data evaluation.

### 9.2.2 Blinding Methods:

The Test Materials as well as the Dosing & Administration and Data Capture forms will be coded by a researcher with respect to treatment, so that subjects and personnel recording data will not be aware of the treatments for which they are reporting. The Study Director will access the codes to identify the Test Materials in the Study Report after completing the data analysis.

### 9.3. Study Material Administration:

Study Materials will be administered to each subject by Carroll-Loye technicians. Test products will be applied volumetrically to the skin surface from a tuberculin (1 ml) syringe, and spread on the site as evenly as possible with two fingertips in a surgical glove, using a light rubbing motion. Skin surfaces to be treated are first cleansed with water and a fragrance free detergent soap, rinsed with a 50% ethanol in water solution, and then towel dried.

# 9.4 Subject Consent:

Written subject consent is an inclusion criterion.

# **9.5** Stop Rule and Medical Management:

Specific adverse reactions in subjects to the test materials are not anticipated based on low acute and chronic toxicity, as well as the research design to minimize exposures, and the training of subjects to aspirate landing mosquitoes before they probe or bite. Because the products are topical, technical personnel will monitor, and subjects will

self-monitor, for allergic and irritant skin reactions, particularly redness, edema, itching or pain, and report any such reactions to the Study Director. Any subject showing adverse skin reactions will immediately stop further participation. The treated skin will be gently washed with clean water and mild soap to remove the test product, and the area will be gently dried with a clean towel. The subject will be removed from further exposure to mosquitoes.

On the day of testing, we will alert the nearest hospital of the scope of our activities in advance of commencing treatment and data collection. In unlikely event of a Type 1 allergic reaction (anaphylaxis), we will contact 9-1-1 by cellular or satellite telephone and cooperate as instructed with emergency personnel. We will be prepared to instruct emergency personnel on how to reach our site via multiple routes. In addition, we will personally transport affected persons to the nearest hospital if so advised by emergency personnel. There is sufficient redundancy in personnel that in such a case subjects remaining at the study site will still receive appropriate technical, scientific and safety guidance.

All subjects are asked to contact the Study Director and a physician of their own choice at any time should they develop a rash (a delayed hypersensitivity reaction) within 48 hours of the conclusion of the test day.

The risk of mosquito-associated health risks is likewise regarded as very low due to the complementary precautions outlined herein. However, the Study Director will assess skin condition of affected subjects should any bites inadvertently occur during efficacy testing. In addition, subjects will be asked to make contact with Study Director at any time should they have health concerns relating to their participation in the efficacy testing.

As part of Medical Management, the Study Director will record all benign and adverse health observations.

# 9.6 Subject training for research with mosquitoes

Approximately one week to four days before repellent efficacy testing, subjects will be trained by technical personnel in handling mechanical

aspirators and observing mosquitoes in the laboratory. Subjects will be shown how to turn on and manipulate the aspirator to capture mosquitoes by a technician who first demonstrates the following procedure, which subjects then emulate: Two laboratory-reared, disease-free female mosquitoes are released in a cage. A small area (less than ½ of the forearm) is uncovered and exposed in the cage, with no insect repellent applied. Subjects will learn how to watch approach and land on the arm, how to detect a mosquito's intention to bite, and how to quickly remove LIBing mosquitoes with the aspirator. A technician will be present to instruct and guide throughout; mosquitoes will not be exposed to more than one subject before being destroyed. This training will be documented. This 'hands-on' experience will assist subjects in collecting data accurately and handling mosquitoes safely during the repellent efficacy trial.

### 10 TEST VARIABLES AND THEIR MEASUREMENT:

#### **10.1** Variables to be Measured:

Subject forearm and lower leg surface area.

Subject self-dosing behaviors.

Weight of test materials delivered to the surrogate skin (gauze) dosimeters.

Number of mosquito lites with intent to bite (LIBes) on the treated surface.

#### 10.2 When Variable will be Assessed:

Dosage will be calculated on the basis of surface area of the lower limb skin that is treated. Measurements to calculate that surface area will be made on each subject in advance of application of the test materials.

Self-dosing behavior (distance of spray nozzles from skin, number of pumps or sweeps of delivery apparatus) will be measured at least three days prior to Test Day 1.

Passive dosimeters (described in section 10.1.3) will be weighed before application of the test materials and again between one and five minutes after application of the test materials.

Subjects will record any 'lites with intent to bite' (LIBes) as they occur. Data are recorded in one minute exposures at 15 minute intervals. The time at which the application of a treatment is completed is recorded as  $t_0$  ('time zero'). There may be a delay of no more than 10 minutes after treatment until exposure begins. Subjects will practice removing mosquitoes exhibiting LIBes before the field test.

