# 10.3.4. Lotion sampling

The amount of lotion applied to limbs will be quantified in a series of three applications analogous to the Spray Sampling above. However, dosimeters are not required, nor are the

extensive practice sessions. The amount applied is the weight difference in the dispensing tube before and after application.

The instructions are as follows:

"Put a new latex glove on each hand. You will apply lotion to one arm only. The technician will tell you to which arm to apply. You will begin with an amount that you suppose is about one half of what you will need to achieve thorough and uniform coverage. After spreading that around the lower part of your arm, you will apply more as needed to the area closer to your elbow. Begin by gently squeezing lotion from a tube with the cap open directly onto the horizontally-held surface of the opposite arm. Hand the tube to the technician. Using the tips of the index and middle fingers, spread the lotion as evenly as possible on all surfaces of the lower arm. Do not spread it onto the hand or beyond the marking on your wrist. If you have sufficient lotion left to spread it evenly and thoroughly toward the elbow, continue in the direction. Do note spread it beyond the elbow or past beyond the marking near the elbow. If you need more lotion to achieve thorough and even coverage, make sure you have wiped all repellent from your fingertips onto the skin and ask the technician to hand you the tube. Apply as much additional as you think you need, as before, but to complete the coverage. If you decide that you have applied more repellent that you would normally use to achieve thorough and even coverage, immediately have the technician wash and dry the treated arm so that none of the repellent you have applied is visible on close inspection, and begin again. Likewise, be careful to avoid dropping any lotion off of the arm, and if this happens, begin again as you would if you applied too much.

After you have completed an application successfully, the technician wash and dry the treated arm so that none of the repellent you have applied is visible on close inspection, and reweigh the tube. You will continue until you have completed three successful applications. Then you will repeat the entire procedure above, but with the lower leg."

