# 11.3.1 Dosimetry:

Dosage will be calculated per square centimeter of skin. The amount of test material delivered to each dosimeter in each trial will be calculated as:

weight after application – weight before application

The **total captured** by all treated dosimeters per trial will be calculated by adding the mass changes in all four dosimeters together, and then subtracting or adding, respectively, any total gain of loss of weight in the paired control dosimeters.

The **proportion covered** of the total limb surface area by the dosimeters is:

Surface area of a set of 4 dosimeters
Surface area of the limb

The estimated **dosage per trial** is: **Total captured** x 1/**proportion covered** 

The specific gravity of each test material will be measured and used to convert the dosage weight data to volumes for preparing individual subject doses volumetrically for dispensing from the tuberculin syringes.

Subject means and standard deviations will be calculated for all measures of dosimeter weight changes as well as application behaviors (distance from nozzle to skin, duration of application, number of sweeps/pumps). Lotion, pump spray and aerosol statistics will be calculated separately and then compared with nonparametric tests for two- and three- sample independent cases (Wilcoxon match-pairs signed-rank and Kruskal-Wallis tests, respectively).

We will statistically assess the strength of any individual subject differences in application behavior and dosing in interaction with the three test materials using Friedman two-way analysis of variance subject dose means for each test material. We will use subject dose means for each test material to calculate dosing grand means (± SD) for each test material. Those means, expressed as repellent weight per unit skin surface area, will be used to determine individual subject doses in the field repellency test.

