# Appendix 1. Test repellent formulations.

# Insect Repellent Spray with IR3535® (EUS26-15)

Ingredients	INCI	[%]	CAS No.	EPA Inert List
Phase A				
IR3535®	Ethyl Butylacetylamino- propionate	20.00	52304-36-6	Active Ingredient
Carbowax 400 /Union Carbide	Polyethylene glycol 400	5.00	25322-68-3	4B
Arlamol E	PEG-15 Stearyl Ether	1.00	25231-21-4	4B
Phase B				
Ethanol SD 40B	Denatured Alcohol	35.00	61116-08-3	4B
Carbowax 1450 /Union Carbide	Polyethylene glycol 1500	4.00	25322-68-3	4B
PVP/VA Copolymer E- 735 /ISP	PVP/VA copolymer	2.00	25086-89-9 64-17-5	
Polysorbate 20 / Uniquema	Tween 20	1.50	9005-64-5	4B
Water, demineralized	Aqua (Water)	31.50	7732-18-5	4A

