# Insect Repellent Aerosol with IR3535® (EUS26-16)

Ingredients	INCI	[%]	CAS No.	EPA Inert List
Phase A				
IR3535®	Ethyl Butylacetylamino- propionate	20.00	52304-36-6	Active Ingredient
Phase B				
Ethanol SD 40B	Denatured Alcohol	21.67	61116-08-3	4B
Propylene glycol / Union carbide	Propylene glycol	4.34	57-55-6	
PVP/VA Copolymer E- 735 /ISP	PVP/VA copolymer	1.73	25086-89-9 64-17-5	
Water, demineralized	Aqua (Water)	17.26	7732-18-5	4A
Phase C				-
A31, Isobutane /Aeropres	Isobutane	35.00	75-28-5	

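### Spray dosimeters are weighed 1 to 5 minutes after spraying with no correction for solvent loss, and the aerosol's dispensing basis is unstated, so spray and lotion amounts may not be on one basis

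*Combined protocol and SAP*

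**What the plan says.** **Sprays.** Under 10.2 the dosimeters "will be weighed before application of the test materials and again between one and five minutes after application of the test materials". Section 11.3.1 takes "weight after application – weight before application" for each dosimeter and adds the four results. It adjusts the total by "subtracting or adding, respectively, any total gain of loss of weight in the paired control dosimeters", then multiplies by the reciprocal of the proportion of limb area covered. Under 10.3.3 only one arm is sprayed per trial, so the control dosimeters on the other arm carry no product.

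**From weight to field dose.** Section 11.3.1 has the specific gravity of each test material measured and "used to convert the dosage weight data to volumes for preparing individual subject doses volumetrically". Section 9.3 has the product applied from a 1 ml syringe. Section 10.3.6 sets each subject's amount as limb area times the grand-mean dosimetry rate for that product.

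**Lotion.** Section 10.3.4 uses no dosimeters: "The amount applied is the weight difference in the dispensing tube before and after application".

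**Composition (Appendix 1).** The pump spray contains 35.00% "Ethanol SD 40B" and 31.50% water. The aerosol contains 21.67% ethanol, 17.26% water and 35.00% "A31, Isobutane /Aeropres". Both contain 20.00% active.

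Section 8.3.2 itself expects the carrier in both sprays to evaporate. No recovery or evaporation correction appears anywhere. Section 10.3.3 has the spray containers weighed before and after each application, but 11.3.1 does not use those weights in the dose.

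**The concern.** The dosimeter weight is read while a volatile product may be drying, and it is then treated as a weight of undried product. The control dosimeters can correct for moisture or handling changes in the gauze. They cannot correct for ethanol leaving a wet dosimeter. Because the captured weight is multiplied by a fixed area ratio, a fractional loss on the gauze becomes the same fractional loss in the calculated dose. The wait is allowed to vary fivefold, so the loss can also differ between dosimeters, trials and subjects.

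Three things are at stake.

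- Section 6.1.4 calls dosage determination a main objective, and the field dose is meant to reflect what subjects apply.
- Section 11.3.1 plans to compare lotion, pump and aerosol dosimetry statistics with nonparametric tests. Part of any spray-lotion difference could come from the way the amounts were measured.
- Section 5.2 carries the same dosimetry values into the companion tick study, EMD-003.

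**Working it through.** The plan states no dose, evaporation rate or recovery, so there is no figure of its own to reproduce. The check is a mass balance on Appendix 1.

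**Inputs.** The pump percentages sum to 20 + 5 + 1 + 35 + 4 + 2 + 1.5 + 31.5 = 100.00. The aerosol percentages sum to 20 + 21.67 + 4.34 + 1.73 + 17.26 + 35 = 100.00. Let f be the fraction of ethanol lost between spraying and weighing. The documents do not give f, so the range 0 to 1 is shown.

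**Pump.** If mass D lands on the gauze, the weighed mass is D(1 − 0.35f). Re-dispensed as undried product at 20% active, it delivers 0.20·D(1 − 0.35f), against 0.20·D deposited. The ratio is 1 − 0.35f.

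**Aerosol, propellant-free throughout.** Assume the isobutane has gone before weighing, and that the syringe liquid and its specific gravity are both propellant-free. Per 100 parts of product, 65 parts remain, of which 20/65 = 30.8% is active and 21.67/65 = 33.3% is ethanol. The ratio is 1 − 0.333f.

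| f (assumed) | Pump | Aerosol, propellant-free |
|---|---|---|
| 0 | 1.000 | 1.000 |
| 0.10 | 0.965 | 0.967 |
| 0.25 | 0.912 | 0.917 |
| 0.50 | 0.825 | 0.833 |
| 1.00 | 0.650 | 0.667 |

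Each 10 percentage points of ethanol lost therefore costs 3.5% (pump) or 3.3% (aerosol). The same figures apply to a difference in loss between two dosimeters weighed at different times. Water loss would add to this. The outer bound, with all ethanol and water gone, is 1 − 0.35 − 0.315 = 0.335 for the pump and 1 − (21.67 + 17.26)/65 = 0.401 for the aerosol.

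**Aerosol, specific gravity of the full product.** Suppose the weight is converted with the specific gravity of the full product but the syringe holds propellant-free liquid. The ratio becomes (1 − 0.333f)·R, where R is the density of the propellant-free liquid divided by that of the full product. No densities are given. If the propellant is the lighter part (an assumption), R exceeds 1 and works against the ethanol loss. Break-even is R = 1/(1 − 0.333f), which is 1/0.917 = 1.09 at f = 0.25 and 1/0.833 = 1.20 at f = 0.50. Above break-even, the aerosol would be over-dispensed relative to the deposit.

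**Lotion.** Tube weighing has no evaporation term. Under 10.3.4 the lotion is spread with gloved fingertips, so any residue left on the glove is counted as applied.

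**The case against.** **The size is not shown.** Section 8.3.2 says the carrier evaporates but not how fast. Five minutes is short, and outdoor exposure covers only part of the wait: dosimeters are taken off for weighing (10.3.3), and 10.4 names the main building as well as the terrace. This stands. A reader might infer that the sprays are known to be dispensed about a third low. The documents do not support that, because the ranges start at no error.

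**The aerosol figure could be made to look much worse.** If the weight were re-dispensed as whole product at 20% active, the ratio would be 0.65 − 0.2167f, or 0.65 falling to 0.433. That requires syringe liquid that keeps its 35% isobutane while the gauze has lost all of it. The protocol does not describe this, so the figure should not be used.

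**No comparison of CPT between products is planned.** This also stands. Section 11.3.2 aims at a mean and standard deviation for each material, and the products already differ in active content (lotion 10%, sprays 20%). The planned comparison that is affected is that of the dosimetry statistics in 11.3.1. A dose below the amount applied would tend to shorten spray CPT, which is conservative for a protection claim.

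**The sections set different methods for different product forms and do not contradict one another in wording.** This is fair. The difficulty is that 11.3.1 then compares and dispenses the results as if they were one quantity.

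**A single weighing time is impractical.** Section 10.3.5 has eight dosimeters per replicate and names one balance for them. The window is 4 minutes, or 240/8 = 30 seconds each. This stands and shapes the fix.

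**Conclusion.** The point holds as a measurement flaw of unknown size. For the pump spray, evaporation before weighing can only lower the measured amount, the control dosimeters cannot detect it, and nothing else in 11.3.1 corrects it. The active re-dispensed is 1 − 0.35f of that deposited. For the aerosol it is 1 − 0.333f on a fully propellant-free basis. Because the protocol does not state that basis, neither the net aerosol error nor its direction is established. These ratios are scenarios over an assumed f, with water loss ignored and all propellant taken as gone before weighing. They are not estimates of what will happen.

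The consequences are limited to three: a spray field dose that may not be the amount subjects apply, a dosimetry comparison on mixed bases, and the transfer of the same values to the tick study. The documents do not support reading this as proof of a large under-dose, as an invalid comparison of CPT between products, or as a lotion measurement free of error. The point should be settled before dosimetry is final, and it does not undermine the design as a whole.

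**What to change.** Reconcile 10.2, 10.3.4 and 11.3.1 so that measured and dispensed amounts share one stated basis for each product.

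- Record the time from application to weighing for every dosimeter, and narrow the window where practical.
- Before dosimetry is final, load dosimeters on the bench with known masses of each spray liquid (propellant-free for the aerosol). Weigh them across the same window and conditions, and apply the measured recovery in 11.3.1.
- Measure specific gravity on the liquid that actually goes into the syringe, and state for the aerosol that this is what was done.
- Use the container weights from 10.3.3 only as an upper-bound plausibility check. They include spray that misses the limb and, for the aerosol, the propellant.

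The cost is a short bench run with existing balances and materials, one added factor in 11.3.1, and a small delay before the dosimetry values are final. No dose is proposed.
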